- History of hemochromatosis or iron overload as defined by the presence of 3+ or 4+ stainable iron on screening liver sample collection (archival or fresh)
- Drug-induced liver disease as defined on the basis of typical exposure and history
- Known bile duct obstruction
- Active history of any other type of liver disease (e.g., liver cancer) other than NASH
- Estimated glomerular filtration rate (eGFR) <60 mL/min/1.73m²
- History of biliary diversion
- Liver enzymes (ALT, AST) levels >5× upper limit of normal (ULN) at screening. In addition to the two baseline measurements, levels may be repeated once more at the discretion of the investigator during the screening period, and the average of the three readings will be used.
 - Alkaline phosphatase > 2 × ULN at screening. Levels may be repeated once at the discretion of the investigator during the screening period, and the lower of the two readings may be used.
 - Total bilirubin > ULN at screening. Patients with a history of Gilbert's syndrome may have direct bilirubin measured and would be eligible for this study provided the direct bilirubin level is ≤ ULN; and the subject has normal transaminases, alkaline phosphatase, hemoglobin and reticulocyte count.
- History of eating disorders *within 2 years prior to randomization*
[REDACTED]
[REDACTED]
[REDACTED]
- Weight gain >10% or loss >5% within 3 months prior to randomization

- For patients with qualifying archival liver biopsies, stable (within 5%) body weight will be required from the time of the biopsy to randomization or 3 months prior to randomization, whichever is longer
- History of procedures for weight loss (e.g., lap band (unless the lap band or balloon was removed and the weight is stable for at least 3 months prior to screening) or gastric bypass)
- Planned medical procedure or surgery during the study *that in the investigator's opinion would interfere with participant safety, achieving the study objectives or compliance with the protocol*
- Patients with osteoporosis (T-score of -2.5 or lower)
- History of fracture, bone surgery (e.g., hardware placement, joint replacement, bone grafting, or amputation), or clinically significant bone trauma within 8 weeks of screening
- Vitamin D deficiency (25-hydroxy vitamin D level <20 ng/mL) unless high-dose vitamin D (e.g., 50,000 IU weekly × 6 weeks) is initiated prior to randomization, and vitamin D Institute of Medicine 2011 recommendations (800–2000 IU/day) are followed throughout the study.

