4.6 TREATMENT, PATIENT, STUDY, AND SITE DISCONTINUATION

4.6.1 Study Treatment Discontinuation

Patients must permanently discontinue study treatment if they experience any of the following:

- Any medical condition that the investigator or Sponsor determines may jeopardize the patient's safety if he or she continues to receive study treatment
- Investigator or Sponsor determination that treatment discontinuation is in the best interest of the patient
- Pregnancy
- Any adverse event CTCAE Grade 4 or higher, regardless of attribution to study drug
- Positively detected suicidal ideation type 4 or 5 or suicidal behavior
- 24-hour urinary cortisol $>1.5 \times$ ULN and $>2 \times$ baseline, if confirmed on follow up visit within 2 weeks.
- If any signs or symptoms of hyper- or hypothyroidism that accompany changes in thyroid function tests (TSH or free T4) that are confirmed by repeat testing.
- Abnormal IGF-1 that is confirmed by repeat testing.
- Nontraumatic bone fracture

The primary reason for study treatment discontinuation should be documented on the appropriate eCRF. Patients who discontinue study treatment prematurely will not be replaced. Patients who discontinue treatment prior to study treatment completion will participate in the end-of-treatment visit at the time of early discontinuation and will enter a follow-up period for a total of 6 weeks.

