| In patients with BLM of ALT and AST $<1.5 \times$ ULN: If ALT or AST $>3 \times$ ULN or TBL $>1.5 \times$ BLM OR In patients with BLM of ALT or AST $>1.5 \times$ ULN: If AST or ALT $>2 \times$ BLM or TBL $>1.5 \times$ BLM | 
 Repeat testing of ALT, AST, ALP and TBL within 48–72 hours, with inquiry about symptoms. 
If repeat testing above confirms initial result:
 
 Repeat ALT, AST, ALP, and TBL two or three times weekly. Frequency of retesting can decrease to once a week or less if abnormalities stabilize or the trial drug has been discontinued and the subject is asymptomatic. Obtain a more detailed history of symptoms and prior or concurrent diseases. Obtain a history of concomitant drug use (including nonprescription medications and herbal and dietary supplement preparations), alcohol use, recreational drug use, and special diets. Rule out acute viral hepatitis types A, B, C, D, and E; autoimmune or alcoholic hepatitis; NASH; hypoxic/ischemic hepatopathy; and biliary tract disease. Obtain a history of exposure to environmental chemical agents. Obtain additional tests to evaluate liver function, as appropriate (e.g., INR, direct bilirubin). Consider gastroenterology or hepatology consultations. Consider liver biopsy |

Table 1 Guidelines for Management of Patients Who Experience Specific Adverse Events (cont.)

| Event | Action to Be Taken |
|--|--|
| Increased Liver Enzymes (cont.) | |
| In patients with BLM of ALT and AST $<2 \times$ ULN: If ALT or AST increases to $>5 \times$ BLM | 
 Interrupt or discontinue BFKB8488A. |
| In patients with BLM of ALT and AST $\geq 2 \times$ ULN but $<5 \times$ ULN: If ALT or AST increases to $>3 \times$ BLM | 
 Interrupt or discontinue BFKB8488A. |
| In patients with BLM of ALT and AST $\geq 5 \times$ ULN: If ALT or AST increases to $>2 \times$ BLM | 
 Interrupt or discontinue BFKB8488A. |

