| In patients with BLM in normal range or ALT or AST $<1.5 \times$ ULN: If ALT or AST increases to $>3 \times$ ULN accompanied by: 
 a concomitant increase in TBL to $>2 \times$ ULN 
OR
 
 the INR concomitantly increases by > 0.2 in any patients with signs and symptoms of fatigue, nausea, vomiting, right upper quadrant pain or tenderness, fever, rash, and/or eosinophilia ($> 5\%$) | 
 Interrupt or discontinue BFKB8488A. |
| In patients with BLM of ALT or AST $> 1.5 \times$ ULN: If ALT or AST increases to $>2 \times$ BLM accompanied by: 
 a concomitant increase in TBL to $>2 \times$ BLM 
OR
 
 the INR concomitantly increases by > 0.2 in any patients with signs and symptoms of fatigue, nausea, vomiting, right upper quadrant pain or tenderness, fever, rash, and/or eosinophilia ($> 5\%$) | 
 Interrupt or discontinue BFKB8488A. |
| | 
 In all the above instances, continue monitoring the liver enzymes. If the levels of liver enzymes return to baseline levels, or alternate causes are clearly identified, resumption of dosing may be considered in some cases after discussion with the Medical Monitor. |

BLM=baseline measurement; INR=International Normalized Ratio; TBL=total bilirubin; ULN=upper limit of normal.

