5.2.3 Adverse Events of Special Interest (Immediately Reportable to the Sponsor)

Adverse events of special interest are required to be reported by the investigator to the Sponsor immediately (i.e., no more than 24 hours after learning of the event; see Section 5.4.2 for reporting instructions). Adverse events of special interest for this study are as follows:

- Marked hypertension as defined by a systolic blood pressure ≥ 180 mm of Hg that is at least 20 mm higher than the baseline measurement.
- Weight loss greater than 10% of baseline (Day 1) body weight within a 12-week period at any point in the study
- Glucose measurements, serum or home glucometer readings, ≤ 54 mg/dL
- Symptomatic hypoglycemia causing altered mental status, seizures, or requiring IV dextrose for treatment
- Increases in QT interval, unless there is a clear alternative cause for the changes
 - Sustained (at least 2 ECG measurements > 30 minutes apart) QTcF that is > 500 ms and/or > 60 ms longer than the baseline value
 - Sustained absolute QTcF that is > 515 ms

An episode of torsades de pointes or a new ECG finding of clinical concern
- Cases of potential drug-induced liver injury that include an elevated ALT or AST in combination with either an elevated bilirubin or clinical jaundice, as defined by Hy's Law (see Section 5.3.5.7)
- Suspected transmission of an infectious agent by the study drug, as defined below

Any organism, virus, or infectious particle (e.g., prion protein transmitting transmissible spongiform encephalopathy), pathogenic or non-pathogenic, is

considered an infectious agent. A transmission of an infectious agent may be suspected from clinical symptoms or laboratory findings that indicate an infection in a patient exposed to a medicinal product. This term applies only when a contamination of the study drug is suspected.

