5.3.5.7 Abnormal Liver Function Tests

The finding of an elevated ALT or AST ($>3 \times \text{ULN}$) in combination with either an elevated total bilirubin ($>2 \times \text{ULN}$) or clinical jaundice in the absence of cholestasis or other causes of hyperbilirubinemia is considered to be an indicator of severe liver injury (as defined by Hy's Law). Therefore, investigators must report as an adverse event the occurrence of either of the following:

- Treatment-emergent ALT or AST $>3 \times \text{ULN}$ in combination with total bilirubin $>2 \times \text{ULN}$
- Treatment-emergent ALT or AST $>3 \times \text{ULN}$ in combination with clinical jaundice

The most appropriate diagnosis or (if a diagnosis cannot be established) the abnormal laboratory values should be recorded on the Adverse Event eCRF (see Section 5.3.5.2) and reported to the Sponsor immediately (i.e., no more than 24 hours after learning of the event), either as a serious adverse event or an adverse event of special interest (see Section 5.4.2).

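### With both baseline enzymes above 1.5 and up to 3 × ULN, some potential Hy's Law cases that must be reported within 24 hours meet no liver interruption row in Table 1

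*Combined protocol and SAP*

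**What the plan says.** **Reporting.** Section 5.3.5.7 states that ALT or AST above 3 × ULN with total bilirubin above 2 × ULN, or "clinical jaundice in the absence of cholestasis or other causes of hyperbilirubinemia is considered to be an indicator of severe liver injury". When treatment-emergent, either combination must be reported within 24 hours, whatever the baseline. Section 5.2.3 lists the same event as one of special interest: "Cases of potential drug-induced liver injury that include an elevated ALT or AST in combination with either an elevated bilirubin or clinical jaundice".

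**Interruption.** Five liver rows of Table 1 (Section 5.1.2.3) lead to interruption or discontinuation:

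| Row | Baseline ALT/AST | Trigger |
|---|---|---|
| Enzyme-only 1 | both < 2 × ULN | ALT or AST > 5 × BLM |
| Enzyme-only 2 | both ≥ 2 and < 5 × ULN | ALT or AST > 3 × BLM |
| Enzyme-only 3 | both ≥ 5 × ULN | ALT or AST > 2 × BLM |
| Combined, low baseline | normal, or ALT or AST < 1.5 × ULN | ALT or AST > 3 × ULN with "a concomitant increase in TBL to $>2 \times$ ULN", or with an INR rise above 0.2 and symptoms |
| Combined, raised baseline | ALT or AST > 1.5 × ULN | "If ALT or AST increases to $>2 \times$ BLM accompanied by" bilirubin > 2 × BLM, or an INR rise above 0.2 and symptoms |

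**Monitoring.** A separate row requires "Repeat testing of ALT, AST, ALP and TBL within 48–72 hours, with inquiry about symptoms". At baselines above 1.5 × ULN it applies once an enzyme exceeds 2 × BLM or bilirubin exceeds 1.5 × BLM. If the result is confirmed, a work-up follows.

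**Entry limits (Section 4.1.2).** The enzyme exclusion is "Liver enzymes (ALT, AST) levels >5× upper limit of normal (ULN) at screening". Total bilirubin above ULN is also excluded, except in Gilbert's syndrome, and then only if "the subject has normal transaminases, alkaline phosphatase, hemoglobin and reticulocyte count".

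**General stopping rules.** Section 4.6.1 requires discontinuation for "Any adverse event CTCAE Grade 4 or higher, regardless of attribution to study drug" and allows it on investigator or Sponsor judgment. It names no liver criterion.

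**The concern.** The protocol treats one combination of values as a signal of severe liver injury at any baseline, yet ties a written interruption trigger to those values only when baseline enzymes are low. At higher baselines the trigger moves to multiples of the patient's own baseline, and part of the reportable range drops out. Clinical jaundice, the other half of the reporting definition, appears in no liver interruption row at any baseline.

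What is at stake is whether dosing stops by rule while such a case is worked up, or by individual decision. The protocol does write firm rules elsewhere: Section 5.1.2.8 holds study drug until a psychiatric evaluation is done, and Section 4.6.1 requires stopping for confirmed abnormal IGF-1 or urinary cortisol.

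**Working it through.** The plan gives no figure to reproduce; the question is which rows a case can meet. All values are in multiples of ULN.

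**1. Which rows can fire.** Take both baselines above 1.5 and up to 3, one enzyme above 3, and bilirubin above 2.
- The low-baseline combined row does not apply, because neither baseline is below 1.5.
- The raised-baseline combined row needs ALT or AST > 2 × BLM. This governs its INR limb too.
- The enzyme-only rows that can apply need > 5 × BLM or > 3 × BLM. Reading them jointly or enzyme by enzyme makes no difference here.

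So if neither enzyme exceeds 2 × BLM, no row is met.

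**2. Bilirubin is not the obstacle.** Entry requires total bilirubin ≤ 1, and the Gilbert's exception is closed to patients with raised transaminases. With BLM ≤ 1, on-treatment bilirubin above 2 exceeds 2 × BLM. The bilirubin limb of the combined row is met, and so is the retest trigger (> 1.5 × BLM). This takes BLM to be the eligible screening value.

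**3. The uncovered range.** With equal baselines, the higher on-treatment enzyme E is uncovered when 3 < E ≤ 2 × BLM.

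| BLM (both enzymes) | Uncovered E | Rise over baseline (3/BLM up to 2) |
|---|---|---|
| 1.6 | > 3 to 3.2 | 1.88- to 2-fold |
| 1.8 | > 3 to 3.6 | 1.67- to 2-fold |
| 2.0 | > 3 to 4.0 | 1.5- to 2-fold |
| 2.5 | > 3 to 5.0 | 1.2- to 2-fold |
| 3.0 | > 3 to 6.0 | from any rise to 2-fold |

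The lower end of the last line is a formal limit only: 3.01 from a baseline of 3.0 is a trivial change.

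**4. A worked case.** Baseline ALT 2.5, AST 2.0, bilirubin 0.9; on treatment 4.5, 3.8 and 2.5.
- Reporting definition: 4.5 > 3 and 2.5 > 2. Met.
- Raised-baseline combined row: needs ALT > 2 × 2.5 = 5.0 or AST > 2 × 2.0 = 4.0. Not met.
- Enzyme-only row for baselines of 2 to below 5: needs ALT > 3 × 2.5 = 7.5 or AST > 3 × 2.0 = 6.0. Not met.
- Retest row: bilirubin 2.5 > 1.5 × 0.9 = 1.35. Met.

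**5. The same on-treatment values from other baselines.** From 1.4/1.4 the low-baseline combined row is met. From 1.6/1.6 the raised-baseline combined row is met, since 4.5 > 3.2 and 2.5 > 1.8. From 2.5/2.0 none is met.

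**6. Grid check.** The rows were applied to a grid with both baselines above 1.5 and up to 5, wider than the range at issue, keeping cases that met the enzyme and bilirubin cut-offs with neither enzyme above 2 × BLM. None of 326,340 combinations met an interruption row.

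**The case against.** **Baseline multiples look deliberate.** Table 1 splits both the retest and the combined rows by baseline, and patients may enter with enzymes up to 5 × ULN, where 3 × ULN need not mean change. This stands for baselines above 3 × ULN. It is weaker between 1.5 and 3, because bilirubin has also more than doubled from a value that had to be within normal limits, and the documents give no reason for dropping the ULN-based trigger.

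**Dosing can be stopped without a liver row.** A reader might infer that the protocol lets a potential Hy's Law case go on receiving drug unchecked. The documents do not support that:
- Section 4.5 makes each dose conditional on acceptable local laboratory values.
- Section 5.1.2.2 permits suspension for a related event of any grade, and Table 3 in Section 5.3.4 makes relatedness the default.
- Section 5.1.2.3 requires interruption for related Grade 3 events, and Section 4.6.1 requires discontinuation for any Grade 4 event.
- The Sponsor is told within 24 hours and may stop treatment, and the IMC reviews laboratory abnormalities (Section 3.1.2).
- With dosing every 2 weeks and retesting in 48–72 hours, results should usually precede the next dose.

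What survives is narrower. The acceptable values are not defined, suspension is optional, and the grade rules do not refer to this combination. The CTCAE laboratory cut-offs are not printed, so how far the grade rules cover it cannot be settled here.

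**Table 1 may seem to contradict itself.** With baseline ALT 2.5, the printed ALT trigger is > 3 × ULN if baseline AST is 1.4 and > 5 × ULN if it is 1.6. A reader might take this as evidence against any coherent baseline scheme. It rests on 'or' in the low-baseline combined row where the matching retest row has 'and', which is probably a wording slip, so no weight is put on it. Reading 'and' would not close the gap; it would bring in patients with only one enzyme above 1.5.

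**The size is uncertain.** The uncovered range is narrow just above 1.5, the visible text does not define 'treatment-emergent', and no headed risk in Section 5.1.1 is hepatotoxicity (its introduction is partly redacted). These points argue for a modest rating.

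**Conclusion.** The point holds for patients whose baseline ALT and AST are both above 1.5 and up to 3 × ULN. If ALT or AST rises above 3 × ULN without either enzyme exceeding twice its baseline, and bilirubin exceeds 2 × ULN, the case is reportable within 24 hours but meets no liver interruption row. The row logic is certain as printed, given that BLM is the eligible screening value.

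The consequence is less certain. General provisions may well produce a hold; none is a defined trigger for this combination. Neither the share of patients with such baselines nor an event rate is given, so frequency is unknown.

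A reader might extend the gap to baselines of 3 to 5 × ULN, which are eligible. The documents do not support that clearly: those patients already exceed 3 × ULN, so whether the finding is treatment-emergent is arguable. The change is a worthwhile, inexpensive safety improvement and does not call the design or efficacy analysis into question.

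**What to change.** Add one liver row to Table 1 for patients with baseline ALT and AST not above 3 × ULN. Confirmed treatment-emergent ALT or AST above 3 × ULN, with total bilirubin above 2 × ULN or clinical jaundice as Section 5.3.5.7 defines it, leads to temporary interruption pending the listed work-up. Resumption follows the existing clause that requires discussion with the Medical Monitor. Cross-reference Sections 5.3.5.7 and 5.2.3. Leave the other rows unchanged, and keep the BLM-based rows for baselines above 3 × ULN.

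The cost is one table row and two cross-references in an amendment. The laboratory tests are already collected. The downside is a few doses held for cases later explained by cholestasis or another cause.

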5.1.2.4 Injection-Site Reaction/Allergic and Anaphylactic Reactions

Local injection site reactions, will be treated as per local or institutional standard operating procedures. The severity of local reaction, including pain, erythema, tenderness, itching, induration, ulceration, necrosis, etc., should be graded per FDA Guidance on Toxicity Grading Scale for Healthy Adult and Adolescent Volunteers Enrolled in Preventive Vaccine Clinical Trials (see [Appendix 4](#)). Additionally, maximal diameter of individual ISR, duration of symptoms and treatment if any, should be recorded (see Section [5.3.5.1](#) and [Appendix 4](#)).

Guidance for managing anaphylaxis is described in [Appendix 5](#).

5.1.2.5 Loss of Bone Mineral Density Related to Weight Loss

Patients will be closely monitored for bone fractures and discontinued from treatment in the event of non-traumatic bone fractures.

5.1.2.6 Hypoglycemia

Patients will be monitored for signs and symptoms of hypoglycemia and have blood glucose measured at baseline and throughout study. In the event that a patient shows signs or symptoms of hypoglycemia, has one documented blood glucose level of ≤ 54 mg/dL, or has two documented blood glucose levels of ≥ 270 mg/dL, the investigator should use clinical judgement to implement glycemic rescue treatment consistent with the local standard of care. Patients should be advised on the management of hypoglycemia according to local standard of care, and dosage of concurrent antidiabetic medication should be adjusted as necessary. Any treatment administered as part of glycemic rescue should be documented and reported to the Medical monitor immediately (see Section [5.2.3](#)). For patients with blood glucose levels of ≥ 270 mg/dL, continuation of the patient in the study will be determined by the Medical Monitor after discussion with the investigator.

5.1.2.7 Hypothalamic Pituitary Axis

Patients will be monitored for abnormalities in free T4, TSH, IGF-1, ACTH, 24-hour urinary cortisol, and 24-hour urinary creatinine periodically during the study. If a patient is found to have an elevated 24-hour urinary free cortisol [UFC] $> 1.5 \times$ ULN and $> 2 \times$ baseline, a repeat UFC will be performed within two weeks for confirmation. If the confirmatory test is $> 1.5 \times$ ULN and $> 2 \times$ baseline, the patient must be discontinued from BFKB8488A treatment and referred to an endocrinologist for further evaluation and treatment. BFKB8488A will also be discontinued in any patient who develops an abnormal IGF-1 levels, based on age-adjusted values for the population, during the study that is confirmed by a repeat measurement. For any patients who develop abnormalities in TSH and/or free T4 (based on reference values for the population), repeat testing to confirm the increase, followed by further evaluation by an endocrinologist needs to be done. BFKB8488A must be discontinued if any signs or symptoms of hyperthyroidism or hypothyroidism accompany the changes in TSH and/or free T4.

5.1.2.8 CNS Effects and Mood

The effects on CNS and mood will be closely monitored. If a patient has a PHQ-9 score at or above 15 (moderately severe depression), at or above 10 (moderate depression) with a score of 2 or 3 for the question “Thoughts that you would be better off dead, or thoughts of hurting yourself in some way?”, or a C-SSRS suicidal ideation type 4 or 5 or behavior, he/she would be referred for timely psychiatric evaluation and/or discontinued from treatment. Study drug should be held while awaiting psychiatric evaluation. Additional monitoring of anxiety or insomnia may be performed if needed.

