4.5.14 Clinical Outcome Assessments

Patient-reported outcome (PRO) instruments will be completed to assess the treatment benefit and more fully characterize the safety profile of BFKB8488A. In addition, PRO instruments will enable the capture of each patient's direct experience with BFKB8488A.

PRO data will be collected through use of the following instruments: The Columbia-Suicide Severity Rating Scale (C-SSRS), the Patient Health Questionnaire-9 (PHQ-9), and the Appetite Sensations Visual Analogue Scale (VAS).

The C-SSRS is a tool used to assess the lifetime suicidality of a patient as well as any new instances of suicidality. The electronic self-rated version of the C-SSRS will be used to assess suicidal ideation and behavior (SIB) at baseline and monitor for changes in SIB at subsequent visits. For positive scores, the investigator will be alerted and should follow up with the patient to provide the appropriate intervention as soon as possible.

The PHQ-9 will be administered for monitoring of potential depression throughout the study. The PHQ-9 is a self-administered diagnostic instrument that scores each of the 9 Diagnostic and Statistical Manual of Mental Disorders criteria of depression. Following study of construct and criterion validity, the PHQ-9 has been shown as a reliable and valid measure of depression severity (Kroenke et al. 2001).

The Appetite Sensations VAS (see [Appendix 2](#)) consists of eight items with words anchored at each end expressing the most positive and the most negative rating of hunger, satiety, fullness, prospective food consumption, desire to eat something fatty, salty, sweet, or savory. This scale has reproducibility, power, and validity (Flint et al. 2000). The scales have been used with both immediate ("Right Now") and retrospective ("Past Week") recall periods (Womble et al. 2003) and have demonstrated sensitivity to effects of lorcaserin on prospective food consumption (Martin et al. 2011).

PRO instruments will be self-administered at the clinic at specified timepoints during the study [REDACTED]. [REDACTED],

[REDACTED], instruments will be administered before the patient receives any information on disease status, prior to the performance of non-PRO assessments, and prior to the administration of study treatment, unless otherwise specified.

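### For C-SSRS ideation type 4 or 5 or suicidal behavior, Section 4.6.1 requires a permanent stop, but Section 5.1.2.8 allows referral with drug only held

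*Combined protocol and SAP*

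**What the plan says.** Section 4.6.1 (Study Treatment Discontinuation) opens its list with "Patients must permanently discontinue study treatment if they experience any of the following". One of the nine bullets reads "Positively detected suicidal ideation type 4 or 5 or suicidal behavior".

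Section 5.1.2.8 (CNS Effects and Mood) names three triggers: a PHQ-9 total of 15 or more; a PHQ-9 total of 10 or more with a score of 2 or 3 on the self-harm item; and the C-SSRS finding. The sentence ends "or a C-SSRS suicidal ideation type 4 or 5 or behavior, he/she would be referred for timely psychiatric evaluation and/or discontinued from treatment". The next sentence adds "Study drug should be held while awaiting psychiatric evaluation".

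Two other sections bear on how these fit together. Section 5.1.2.3 (Management Guidelines) directs sites to the protocol's management guidelines and names 4.6.1 as the detailed list of events that require discontinuation. Section 5.1.2.2 (Treatment Interruption) leaves a restart to the investigator's judgment when doses were missed because of an ongoing adverse event.

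**The concern.** One finding has two actions. Section 4.6.1 makes the stop mandatory and permanent. In 5.1.2.8 the stop is one option, because the and/or wording means that referral alone satisfies the sentence.

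This is a patient-safety matter. Section 5.1.2.8 is where a site would naturally look after a C-SSRS alert, and Section 5.1.1.7 schedules the C-SSRS every 2 weeks, so the trigger is checked repeatedly in every patient. If the site treats the hold as the complete instruction, the open question is what happens after the evaluation. A restart would breach 4.6.1, yet nothing in 5.1.2.8 would tell the site so.

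**Working it through.** No arithmetic applies, so the check sets the sections side by side.

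| | Section 4.6.1 | Section 5.1.2.8 |
|---|---|---|
| C-SSRS trigger | Ideation type 4 or 5, or suicidal behavior | The same |
| PHQ-9 thresholds | Not listed | Two, in the same sentence as the C-SSRS trigger |
| Action | Permanent discontinuation, mandatory | Referral, discontinuation, or both |
| Before evaluation | Not addressed | Drug held |
| After evaluation | Not applicable, as the stop is permanent | Not stated |

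1. *Is it the same trigger?* Yes. Both sections name ideation types 4 and 5 and suicidal behavior. The only added words are in 4.6.1, which asks that the finding be positively detected and does not define the term.

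2. *Does the hold-and-refer action fit all three triggers?* It fits the two PHQ-9 thresholds, since 4.6.1 does not list them. It does not fit the third. One of the three triggers is on the mandatory list, so the conflict is confined to that one.

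3. *Is this how the protocol treats its other mandatory stops?* No. Apart from two general bullets, 4.6.1 has 9 − 2 = 7 specific triggers. For six of them the later text also directs a stop: Grade 4 events (5.1.2.3), urinary cortisol, thyroid and IGF-1 (5.1.2.7), non-traumatic fracture (5.1.2.5) and pregnancy (5.4.3.1). For cortisol, 5.1.2.7 requires both discontinuation and specialist referral. Suicidality is the only one of the seven for which the later text makes the stop optional.

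4. *Could 4.6.1 mean a stop only after confirmation?* Three of its nine bullets state a confirmation step: cortisol ("if confirmed on follow up visit within 2 weeks"), thyroid ("changes in thyroid function tests (TSH or free T4) that are confirmed by repeat testing") and IGF-1 ("Abnormal IGF-1 that is confirmed by repeat testing"). The suicidality bullet states none. This favors a stop on detection but does not prove it, because those three bullets concern laboratory tests, where repeat testing is the usual form of confirmation.

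5. *Does the confirmation reading remove the conflict?* Not fully. Hold, evaluate, then stop would be a coherent sequence, but 5.1.2.8 never says that a confirmed case must stop. The final step is missing on either reading.

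**The case against.** The strongest reply is that both sections can be followed at once. A site that discontinues and refers complies with each, 5.1.2.3 already points to 4.6.1, and 5.1.2.8 does not say that such a patient may resume. The restart provision in 5.1.2.2 does not mention suicidality and is no basis for overriding a mandatory permanent stop. Much of this stands: 4.6.1 is the better governing text, and the fault is a local inconsistency. It does not remove the point, because 5.1.2.3 does not say that 4.6.1 prevails over the specific guideline, and a mandatory safety stop should not depend on a site choosing the stricter of two texts.

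The reply also limits the consequence, and that part stands in full. A reader might infer that a patient with a positive finding would go on being dosed. The text does not support this, since drug is held while evaluation is pending.

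A reader might also count Section 4.5.14 as a further conflicting instruction, because it says "For positive scores, the investigator will be alerted and should follow up with the patient to provide the appropriate intervention as soon as possible". That sentence covers any positive score, does not single out types 4 and 5, and can include a permanent stop, so it does not contradict 4.6.1.

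Nor does the absence of a citation to 4.6.1 in 5.1.2.8 show much. Sections 5.1.2.5 and 5.1.2.7 do not cite it either, yet they agree with it. The fault lies in the action stated.

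**Conclusion.** The point holds as an internal inconsistency in a safety rule and should be fixed. For one C-SSRS trigger, 4.6.1 requires a permanent stop and 5.1.2.8 makes the stop optional. The residual risk is a restart after evaluation that 4.6.1 forbids, together with different handling of the same event across sites.

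The wording difference is certain. What the sponsor intended is less so, because positive detection is undefined; the conclusion that text is missing does not depend on which intention is right. The documents give no rate for the event, so no patient count can be attached, and nothing here bears on power, type I error or the Week 52 result.

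A reader might infer a wider pattern of conflicting stopping and dosing rules, for example from the lower-dose resumption in 5.1.2.9 set against the bar on dose reductions in 5.1.2.1. The documents do not establish that: the bar is limited to the fixed dose arms, the plan also has a variable dose arm, and the text around the bar is redacted. The finding is confined to the C-SSRS trigger.

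**What to change.** In 5.1.2.8, separate the triggers:

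- For C-SSRS ideation of type 4 or 5, or suicidal behavior: permanent discontinuation per Section 4.6.1, plus timely psychiatric referral.
- For the two PHQ-9 thresholds: keep the present action, with drug held pending evaluation and discontinuation available.

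The cortisol rule in 5.1.2.7 is a ready model for stop-plus-referral wording.

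If the sponsor intends the stop to follow clinical confirmation, add that step to the suicidality bullet in 4.6.1, as the cortisol, thyroid and IGF-1 bullets do, and say in 5.1.2.8 that a confirmed case stops permanently.

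The cost is about one sentence in 5.1.2.8 and, under the second option, a clause in 4.6.1, made by amendment. No new procedure, visit or data item is needed.
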